#### **9.4.5. *Injection-site Reactions***

Injection-site assessments for local tolerability will be conducted, when reported as:

- an AE from a subject, or
- a clinical observation from an investigator.

Reported injection-site reactions will be characterized within the following categories:

- edema
- erythema
- induration
- itching
- pain.

All injection-site reactions reported as AEs will be closely monitored until resolution. The report of a clinically significant AE of injection-site reaction may prompt notification of the sponsor, clinical photography, and referral for dermatologic evaluation and consideration of a skin biopsy and laboratory evaluations (ALT, AST, complete blood count with percent eosinophils, and additional immunogenicity testing).

Investigational site staff will be provided with separate instructions/training on how to evaluate injection-site reactions and their severity in a consistent manner. Photographs of injection-site reactions may be taken in a standardized manner for record-keeping purposes; however, the photographs will not be used to evaluate the severity of injection-site reaction.

#### **9.4.6. Hypersensitivity Reactions**

All hypersensitivity reactions will be reported by the investigator as either AEs or, if any serious criterion is met, as SAEs.

In the event of suspected drug hypersensitivity reactions (immediate or non-immediate) in subjects who experience moderate to severe injection reactions as assessed by the investigator, unscheduled blood samples will be collected for PK and antidrug antibody (ADA) analyses at the following time points:

- as close as possible to the onset of the event
- at the resolution of the event
- 30 ( $\pm 3$ ) days following the event.

Additionally, unscheduled serum samples for immune safety laboratory testing (including, but not limited to  $\beta$  tryptase, total IgE, complement and cytokine panel testing) should also be collected at approximately 60 to 120 minutes and 4 to 6 weeks after the onset of the event in these subjects.

Instructions for the collection and handling of blood samples will be provided by the sponsor. The actual date and time (24-hour clock time) of each sampling will be recorded.

#### **9.4.7. Safety Monitoring**

The Lilly CP or CRP/scientist will monitor safety data throughout the course of the study.

Lilly will review SAEs within timeframes mandated by company procedures. The Lilly CP or CRP will periodically review the following data:

- trends in safety data
- laboratory analytes including glucose, amylase, and lipase
- serious and nonserious AEs, including AEs of interest (GI events, hypoglycemia, injection-site reactions, hypersensitivity reactions) and reported and adjudicated pancreatitis

Further diagnostic assessments will be recommended whenever lipase and/or amylase are confirmed to be  $\geq 3 \times$  ULN at any visit postdose even if the subject is asymptomatic (as per the algorithm for the monitoring of pancreatic events in [Appendix 7](#)) and, if pancreatitis is suspected, the case will be further defined during an adjudication process.

When appropriate, the Lilly CP or CRP will consult with the functionally independent Global Patient Safety therapeutic area physician or clinical research scientist.

#### 9.4.7.1. Hepatic Safety Monitoring in Subjects with Treatment-emergent Abnormal Liver Tests

*Abnormal liver tests in study participants with normal or near normal baseline ALT, AST, ALP, and total bilirubin (TBL; <1.5× ULN)*

If a subject who was enrolled with baseline ALT, AST, ALP, TBL <1.5× ULN, experiences elevated ALT  $\geq 3 \times$  ULN, ALP  $\geq 2 \times$  ULN, or TBL  $\geq 2 \times$  ULN, liver tests ([Appendix 4](#)) should be repeated within 48 to 72 hours, including ALT, AST, ALP, TBL, gamma-glutamyl transferase (GGT), and creatine kinase (CK) to confirm the abnormality and to determine if it is increasing or decreasing.

If the abnormality persists or worsens, clinical and laboratory monitoring, and evaluation for possible causes of abnormal liver tests should be initiated by the investigator in consultation with the Lilly CP or CRP. Monitoring should continue until levels normalize and/or are returning to approximate baseline levels.

##### *Elevated ALT/AST in subjects with baseline ALT/AST $\geq 1.5 \times$ ULN*

If a subject, who was enrolled with baseline ALT/AST  $\geq 1.5 \times$  ULN, experiences elevated ALT/AST  $\geq 2 \times$  baseline (respectively), liver tests ([Appendix 4](#)) should be repeated within 48 to 72 hours, including ALT, AST, ALP, TBL, GGT, and CK to confirm the abnormality and to determine if it is increasing or decreasing.

If the abnormality persists or worsens, clinical and laboratory monitoring, and evaluation for possible causes of abnormal liver tests should be initiated by the investigator in consultation with the Lilly CP or CRP. Monitoring should continue until levels normalize and/or are returning to approximate baseline levels.

##### *Elevated ALP in subjects with baseline ALP $\geq 1.5 \times$ ULN*

If a subject, who was enrolled with baseline ALP  $\geq 1.5 \times$  ULN, experiences elevated ALP  $\geq 2 \times$  baseline, liver tests ([Appendix 4](#)) should be repeated within 48 to 72 hours, including ALT, AST, ALP, TBL, GGT, and CK to confirm the abnormality and to determine if it is increasing or decreasing.

If the abnormality persists or worsens, clinical and laboratory monitoring, and evaluation for possible causes of abnormal liver tests should be initiated by the investigator in consultation with the Lilly CP or CRP. Monitoring should continue until levels normalize and/or are returning to approximate baseline levels.

##### *Elevated TBL in subjects with baseline TBL $\geq 1.5 \times$ ULN*

If a subject, who was enrolled with baseline TBL  $\geq 1.5 \times$  ULN, experiences elevated TBL  $\geq 1.5 \times$  baseline, liver tests ([Appendix 4](#)) should be repeated within 48 to 72 hours, including ALT, AST, ALP, TBL, direct bilirubin, GGT, and CK to confirm the abnormality and to determine if it is increasing or decreasing.

If the abnormality persists or worsens, clinical and laboratory monitoring, and evaluation for possible causes of abnormal liver tests should be initiated by the investigator in consultation with

the Lilly CP or CRP. Monitoring should continue until levels normalize and/or are returning to approximate baseline levels.

#### **9.4.7.2. Additional Hepatic Data Collection (Hepatic Safety eCRF) in Subjects with Treatment-emergent Abnormal Liver Tests**

*Treatment-emergent abnormal liver tests in subjects with normal or near normal baseline ALT, AST, ALP, and TBL (<1.5× ULN)*

In a subject, who was enrolled with baseline ALT, AST, ALP, and TBL  $< 1.5 \times$  ULN, additional hepatic safety data should be collected, if 1 or more of the following conditions occur:

- elevation of serum ALT to  $\geq 5 \times$  ULN on 2 or more consecutive blood tests
- elevated total bilirubin to  $\geq 2 \times$  ULN (except for cases of known Gilbert's syndrome)
- elevation of serum ALP to  $\geq 2 \times$  ULN on 2 or more consecutive blood tests
- hepatic event considered to be a SAE

*Elevated ALT/AST in subjects with baseline ALT/AST  $\geq 1.5 \times$  ULN*

In a subject, who was enrolled with baseline ALT/AST  $\geq 1.5 \times$  ULN, elevated ALT/AST  $\geq 3 \times$  baseline (respectively) on two or more consecutive tests should prompt additional hepatic safety data collection.

*Abnormal ALP in subjects with baseline ALP  $\geq 1.5 \times$  ULN*

In a subject, who was enrolled with baseline ALP  $\geq 1.5 \times$  ULN, elevated ALP  $\geq 2 \times$  baseline on two or more consecutive tests should prompt additional hepatic safety data collection.

*Abnormal TBL in subjects with baseline TBL  $\geq 1.5 \times$  ULN*

In a subject, who was enrolled with baseline TBL  $\geq 1.5 \times$  ULN, elevated TBL  $\geq 2 \times$  baseline on two or more consecutive tests should prompt additional hepatic safety data collection.

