**Table GPGQ.2. Child-Pugh Classification**

Parameter	1 point	2 points	3 points
Serum Albumin (g/dL)	>3.5	2.8 to 3.5	<2.8
Total Bilirubin (mg/dL)	<2	2 to 3	>3
Prothrombin Time (sec. prolonged) or	<4	4 to 6	>6
Prothrombin Time INR	<1.7	1.7 to 2.3	>2.3
Ascites a	Absent	Slight	Moderate
Hepatic Encephalopathy b	None	1 or 2 Or current treatment with lactulose or neomycin or other antibiotics	3 or 4 Or continued encephalopathy while receiving treatment with lactulose and/or neomycin or other antibiotics

**Child-Pugh A (mild): 5 or 6 points; Child-Pugh B (moderate): 7 to 9 points; Child-Pugh C (severe): 10 to 15 points.** Adapted from Child and Turcotte (1964) and Pugh et al. (1973).

Abbreviations: INR = international normalized ratio.

a Absent: no detectable ascites.

Slight: no distension; ascites are only detectable by ultrasound examination.

Moderate: ascites causing moderate symmetrical distension of the abdomen.

b Grade 0: normal consciousness, personality, neurological examination, electroencephalogram.

Grade 1: restless, sleep disturbed, irritable/agitated, tremor, impaired handwriting, 5 cycles per second waves.

Grade 2: lethargic, time-disoriented, inappropriate, asterixis, ataxia, slow triphasic waves.

Grade 3: somnolent, stuporous, place-disoriented, hyperactive reflexes, rigidity, slower waves.

Grade 4: unrousable coma, no personality/behavior, decerebrate, slow 2 to 3 cycles per second delta activity.

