- [30] show evidence of significant active neuropsychiatric disease
- [31] have a history of malignancy within 5 years prior to screening
- [32] have a history or presence of pancreatitis (history of chronic pancreatitis or idiopathic acute pancreatitis), elevation in serum amylase and/or lipase  $>1.5 \times$  the upper limit of normal (ULN) or GI disorder (eg, relevant esophageal reflux or gall bladder disease) or any GI disease which impacts gastric emptying (eg, gastric bypass surgery, pyloric stenosis, with the exception of appendectomy) or could be aggravated by GLP-1 analogs or dipeptidyl peptidase-IV inhibitors. Subjects with dyslipidemia and subjects who had cholecystolithiasis treatment (removal of gall stones) and/or cholecystectomy (removal of gall bladder) in the past, with no further sequelae, may be included in the study at the discretion of the investigator.
- [33] have serum AST or ALT  $>2 \times$  ULN or total bilirubin  $>1.5 \times$  ULN (applies to Group 1 control subjects only)
- [34] have a serum triglyceride  $\geq 5$  mmol/L (442.5 mg/dL) at screening (applies to Group 1 control subjects only)
- [35] show evidence of human immunodeficiency virus (HIV) infection and/or positive HIV antibodies
- [36] show evidence of hepatitis C and/or positive hepatitis C antibody (applies to Group 1 control subjects only)
- [37] show evidence of hepatitis B and/or positive hepatitis B surface antigen (applies to Group 1 control subjects only)
- [38] are women with a positive pregnancy test or women who are lactating
- [39] regularly use known drugs of abuse and/or show positive findings on urinary drug screen that are not otherwise explained by permitted concomitant medications
- [40] intend to use:
  - a. over-the-counter medication within 7 days prior to dosing (except for hepatic impairment and T2DM subjects on stable doses)
  - b. prescription medication (other than those listed in Section 7.7 and [Appendix 9](#)) within 14 days prior to dosing
  - c. herbal preparations within the 14 days prior to screening

If any of the above situation arises, an otherwise suitable subject may be included at the discretion of the investigator.

- [41] have donated more than 450 mL blood, including plasma and platelets, within 1 month prior to Check-in

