9.5.8 Hepatic Monitoring

If a subject experiences elevated alanine aminotransferase (ALT) $\geq 3 \times$ upper limit of normal (ULN), alkaline phosphatase (ALP) $\geq 2 \times$ ULN, or elevated total bilirubin (TBL) $\geq 2 \times$ ULN, liver tests will be performed to confirm the abnormality. Additional safety data may be collected if required, as defined in the protocol. Where applicable, the following will be presented.

The subjects' liver disease history and associated person liver disease history data will be listed. Any concomitant medication of acetaminophen/paracetamol will be listed. Results from any hepatic monitoring procedures, such as a magnetic resonance elastography (MRE) scan, and a biopsy assessment will be listed, if performed.

Hepatic risk factor assessment data will be listed. Liver related signs and symptoms data will be summarized by group and listed. Alcohol and recreational drug use data will also be listed.

All hepatic chemistry, hematology, coagulation, and serology data will be listed. Values outside the reference ranges will be flagged on the individual subject data listings.

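### A hepatic SAE prompts the hepatic-safety eCRF only when all four baseline liver tests are below 1.5×ULN, so hepatic detail is collected unequally and then summarised by group

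*Protocol*

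**What the plan says.** Protocol 9.4.7.2 divides subjects by baseline liver tests. For those whose ALT, AST, ALP and total bilirubin (TBL) were all below 1.5×ULN at enrolment, "additional hepatic safety data should be collected, if 1 or more of the following conditions occur". Three of the four conditions are laboratory values. The fourth is "hepatic event considered to be a SAE".

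Three further paragraphs cover subjects with raised baseline ALT/AST, ALP or TBL (1.5×ULN or more). Each gives one laboratory trigger, a multiple of baseline. For ALP and TBL it is 2× "baseline on two or more consecutive tests should prompt additional hepatic safety data collection"; for ALT/AST the multiple is 3×, also on consecutive tests. None mentions an SAE.

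SAP 9.5.8 gives a single set of ULN-based thresholds for any subject, leaves the collection of additional data to the protocol, and then states: "Liver related signs and symptoms data will be summarized by group and listed".

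**The concern.** A subject with liver disease and raised baseline tests can have a serious hepatic event with no doubling or tripling of ALT, AST, ALP or bilirubin. The exclusion criteria in 6.2.2 themselves name variceal bleeding, spontaneous bacterial peritonitis and encephalopathy, none of which is defined by such a rise. Under 9.4.7.2 as written, that event does not prompt the hepatic data set. The same event in a subject with normal baseline tests does.

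The secondary objective compares safety in each impairment group with controls, and the SAP tabulates liver-related signs and symptoms by group. If that table draws on the prompted data, it rests on a collection rule that differs by baseline liver tests. It could then look thinner, event for event, in the groups with more raised baselines.

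**Working it through.** The documents give no figure to reproduce. The check compares the rules and then asks who falls under which.

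**1. Triggers in 9.4.7.2, side by side**

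| Baseline | Laboratory trigger | Hepatic SAE as trigger |
|---|---|---|
| ALT, AST, ALP, TBL all <1.5×ULN | ALT ≥5×ULN on 2 or more consecutive tests; TBL ≥2×ULN, no repeat required (known Gilbert's excepted); ALP ≥2×ULN on 2 or more consecutive tests | Yes |
| ALT/AST ≥1.5×ULN | ≥3× baseline, 2 or more consecutive tests | None |
| ALP ≥1.5×ULN | ≥2× baseline, 2 or more consecutive tests | None |
| TBL ≥1.5×ULN | ≥2× baseline, 2 or more consecutive tests | None |

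No other section extends the SAE trigger to the last three rows. The amendment summary gives the purpose of the restructuring as separating test cut-offs for normal and raised baseline enzymes. That explains the laboratory multiples. It does not address a trigger that is not a laboratory value.

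**2. Can the laboratory triggers stand in for the SAE trigger?** Exclusions [55] and [56] admit impaired subjects with TBL up to 15 mg/dL and ALT just under 6×ULN. At those limits the triggers are 2 × 15 = 30 mg/dL, or just under 3 × 6 = 18×ULN, twice in succession. A serious event need not produce either.

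**3. Who has a raised baseline?** The split is not by group.
- Exclusion [33] ("applies to Group 1 control subjects only") removes controls with AST or ALT above 2×ULN or TBL above 1.5×ULN. It leaves AST/ALT of 1.5 to 2×ULN and sets no ALP limit. Such a control also loses the SAE trigger.
- An impaired subject with all four tests below 1.5×ULN keeps it.
- In the Child-Pugh table, two or three bilirubin points mean TBL of 2 mg/dL or more. That is at least 1.5×ULN when ULN ≤ 2/1.5 = 1.33 mg/dL. The documents give no ULN, so the range is an assumption:

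| Assumed ULN (mg/dL) | 1.5×ULN | Is 2 mg/dL at or above it? |
|---|---|---|
| 1.0 | 1.50 | yes |
| 1.2 | 1.80 | yes |
| 1.3 | 1.95 | yes |
| 1.4 | 2.10 | no |
| 1.5 | 2.25 | no |

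**4. Is a raised bilirubin more likely in higher Child-Pugh classes?** Enumerate every combination of points (five items, 1 to 3 points each, 3⁵ = 243) and count those with at least 2 bilirubin points. Repeat with encephalopathy capped at 2 points, because exclusion [52] removes Grade 2 or higher.

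| Class | All combinations | Encephalopathy at most 2 points |
|---|---|---|
| A | 1/6 (17%) | 1/6 (17%) |
| B | 45/90 (50%) | 40/75 (53%) |
| C | 116/147 (79%) | 67/81 (83%) |

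These are unweighted counts of score patterns, not proportions of patients. They show direction only. A class C subject can score up to 12 points (13 without the cap) with bilirubin below 2 mg/dL, so not every severe subject loses the trigger. Raised ALT, AST or ALP would put further subjects in the raised-baseline branches.

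**5. SAP against protocol.** The SAP was written from the protocol dated 01 April 2019 and approved in May 2019. Amendment (a) was approved in July 2019. SAP 9.5.8 therefore knows nothing of the baseline strata on which its by-group summary now depends.

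**The case against.** The strongest reply is that little is lost. Under 9.2.1 every SAE in a dosed subject is reported within 24 hours of investigator awareness, whatever the baseline tests. Under 9.2 serious AEs are followed until they resolve, stabilise or are explained. SAP 9.5.1 lists SAEs and summarises treatment-emergent AEs by group. All of this stands. A reader might infer that hepatic SAEs go unrecorded in Group 4, or that the secondary endpoint is biased. The documents support neither: the endpoint is the incidence of AEs, and this rule does not touch it.

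Second, 9.4.7.2 sets prompts and does not forbid collection in other cases. A raised-baseline subject whose event also meets a laboratory trigger is covered. Section 9.4.7.1 has lower thresholds for repeat testing, and Appendix 4 tests may be done for any treatment-emergent hepatic abnormality. This also stands, but it leaves the extra data on a hepatic SAE to discretion in one stratum and to a rule in the other.

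Third, SAP 9.5.8 applies where applicable and does not say that its signs-and-symptoms summary comes only from prompted forms. No inferential safety analysis is planned, and hepatic SAEs should be few with a single dose and up to 30 subjects. That limits the consequence. It does not explain the omission, for which the documents give no reason.

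**Conclusion.** The gap is real and small. As written, a hepatic SAE prompts the additional hepatic data only in subjects with all four baseline tests below 1.5×ULN. In any other subject it does so only if a consecutive-test rise to 2× or 3× baseline accompanies it. What can be lost is hepatic-specific detail, not the event.

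No number of affected events can be given, because the documents state no expected hepatic SAE rate and no baseline distribution. That the loss falls mainly on moderate and severe subjects is an inference from the Child-Pugh bilirubin bands, and it assumes a bilirubin ULN of at most 1.33 mg/dL. It would be tempting to say that controls are captured and most severe subjects are not. The documents do not support that: the rule divides by baseline tests, some controls lose the trigger, some impaired subjects keep it, and the pattern counts are not prevalences.

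The change is worth making because it costs almost nothing and, in a study this small, complete data on each hepatic SAE are useful.

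**What to change.** - **Protocol 9.4.7.2:** take the hepatic-SAE trigger out of the normal-baseline list and state it on a separate line that applies to every subject regardless of baseline tests. Leave all laboratory thresholds unchanged.
- **SAP 9.5.8:** replace the single ULN-based rule with a reference to the amended 9.4.7.1 and 9.4.7.2. Add a footnote to the by-group summary saying that laboratory-triggered collection differs by baseline stratum.
- **Keep the by-group summary as it is.** Restricting it to hepatic SAEs would discard laboratory-triggered subjects and could leave it almost empty with about 6 subjects per group.

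The cost is one line in the protocol, a short edit to the SAP and a few more hepatic-safety forms. The eCRF already exists, and patient management does not change.

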### **9.5. Pharmacokinetics**

At the visits and times specified in the Schedule of Activities (Section 2), venous blood samples of approximately 3 mL each will be collected to determine the plasma concentrations of tirzepatide. A maximum of 3 unscheduled samples may be collected at additional time points during the study if warranted and agreed upon between both the investigator and sponsor. Instructions for the collection and handling of blood samples will be provided by the sponsor. The actual date and 24-hour clock time of each sampling will be recorded.

#### **9.5.1. Bioanalysis**

Samples will be analyzed at a laboratory approved by the sponsor and stored at a facility designated by the sponsor.

Concentrations of tirzepatide will be assayed using a validated liquid chromatography tandem mass spectrometry method.

Bioanalytical samples collected to measure investigational product concentrations will be retained for a maximum of 2 years following last subject visit for the study. During this time, samples remaining after the bioanalyses may be used for exploratory analyses such as metabolism work, protein binding, or bioanalytical method cross-validation.

## 9.6. Pharmacodynamics

### 9.6.1. Immunogenicity Assessments

For immunogenicity testing, venous blood samples of approximately 10 mL will be collected from each subject according to the Schedule of Activities (Section 2) to determine antibody production against LY3298176. Additional samples may be collected if there is a possibility that an AE is immunologically mediated. All samples for immunogenicity testing should have a time-matched sample for PK analysis where relevant. In the event of drug hypersensitivity reactions (immediate or non-immediate), additional samples will be collected as close to the onset of the event as possible, at the resolution of the event, and 30 ( $\pm$  3) days following the event. Instructions for the collection and handling of blood samples will be provided by the sponsor. The actual date and 24-hour clock time of each sampling will be recorded.

Immunogenicity will be assessed by a validated assay designed to detect ADA in the presence of LY3298176. Antibodies may be further evaluated for their ability to neutralize the activity of LY3298176. Positive LY3298176 ADA samples may also be tested for cross-reactivity with native GLP-1 and GIP, and, if positive, may then be tested for neutralizing antibodies against native GLP-1 and GIP.

All subjects will have an ADA sample measured at early discontinuation or at the follow-up visit. A risk-based approach will be used to monitor subjects who develop treatment-emergent ADA (TE ADA), defined as a titer 2-fold (1 dilution) greater than the minimum required dilution of the assay if no ADA were detected at baseline, or a 4-fold (2 dilutions) increase in titer, compared to baseline, if ADA were detected at baseline. The minimum required dilution of the ADA assay is 1:10.

Clinically significant TE ADA will be defined as any TE ADA at the last visit with:

- a high titer ( $\geq$ 1280) or an increasing titer from last measured value
- an association with a moderate-to-severe injection-site reaction
- cross-reactive and/or neutralizing binding of an ADA with endogenous GLP-1 or GIP.

Subjects who have clinically significant TE ADA at early discontinuation or at the follow-up visit should be followed with ADA testing every 3 months for approximately 1 year or until the ADA titers have returned to the baseline ADA titer (defined as ADA titer within 2-fold of baseline). A PK sample may be collected at the follow-up immunogenicity assessment(s), if warranted and agreed upon by the investigator and sponsor.

Every attempt should be made to contact subjects for the follow-up immunogenicity assessment; however, if subjects are unwilling or unable to return for the visit, this is not considered a protocol deviation.

Subjects followed for at least 1 year after dosing who have not returned to baseline, as defined above, will be assessed for safety concerns and, if no clinical sequelae are recognized by the clinical team, no further follow-up will be required. Subjects who have clinical sequelae that are considered potentially related to the presence of TE ADA may also be asked to return for additional follow-up testing.

Samples will be retained for a maximum of 15 years after the last subject visit, or for a shorter period if local regulations and IRB allow, at a facility selected by the sponsor. The duration allows the sponsor to respond to future regulatory requests related to the tirzepatide. Any samples remaining after 15 years will be destroyed.

